1.1 Metastatic spinal cord compression

Metastatic spinal cord compression (MSCC) is a feared complication of metastases to the vertebra. Approximately 5-10 percent of patients with metastatic cancer experience MSCC, most commonly patients with lung-, breast-, prostate and renal cancer.¹ MSCC is a disabling condition that can lead to pain, disablement of sensory and motor function distal to the injury.² Early detection and onset of treatment is key to improve outcome results. Diagnosis is typically set through either CT or MRI scan; however, MRI is the preferred modality for diagnosing.³ Symptoms are severe, unremitting pain, progressive discomfort, sensory symptoms, function deficits and bladder or bowel dysfunction⁴. Treatment is mainly high dose steroids to decrease edema and radiotherapy. Surgery is offered, when possible, to patients in good performance status and followed by radiotherapy². Interventions mainly aim at pain relief and preserving motor functions. A small fraction of patients with highly chemo-sensitive tumors are offered chemotherapy.⁴ The performance status at the time of diagnosis is the main determining factor of the post-treatment outcomes, with patients with lower-extremity function and sensation at the onset of treatment having a longer survival time⁴. When MSCC is diagnosed, life expectancy is typically short, with a 2-year survival of approximately 10% and a median survival of less than 6 months.^{2,5} As treatment is palliative Quality of Life (QoL) is important, however, patients may experience early toxicity after radiotherapy, paradoxically causing reduced QoL.^{5,6}

1.2 Radiotherapy treated MSCC and early gastro-esophageal toxicity

There are only few reports in the literature of gastro-esophageal toxicity after radiotherapy for MSCC. In the recent SCORAD trial, 694 patients were randomized to single or five fraction radiotherapy for MSCC⁷. It was a non-inferiority trial and the primary outcome was ambulatory at 8 weeks. Only half the patients were eligible for the intention to treat analysis that showed no difference between the groups. Almost half of the patients were in performance stage III-IV and 60% had metastases in the thoracic spine. The study reported grade I-II dysphagia in 7- 9%, grade I-II sore

throat in 4-10%, grade I-II nausea in 18% and grade I-II anorexia in 30% of the patients that reached the 8-week evaluation.⁷ In a retrospective report on 1304 patients with MSCC and in another smaller study comparing radiotherapy techniques, Rades et al found no grade 2 or worse early esophageal toxicity and no late toxicity.^{6,8} In a prospective study including 149 patients without spinal compression, treated stereotactically on the spine, Wang et al reported a single patient with grade 3 dysphagia⁹. In a phase III randomized trial comparing short course with split course radiotherapy in 276 patients with MSCC, Maranzano found grade 3 esophagitis or laryngitis in 1,5% of the patients.¹⁰ However, in all these studies patient follow-ups occurred at varying times, typically months apart with no focus on the very early toxicity. In a small prospective study from Rigshospitalet by Gram et al, 30 patients with MSCC treated with 30 Gy in 10 fractions were included¹¹. Patients were followed daily for 3 weeks and hereafter weekly for 4 weeks with telephone interviews and questionnaires. 14 patients were treated at Th8 or above. 11 of the patients treated at Th8 or above reported esophageal discomfort lasting for average 11 days (range 1-18 days). The toxicity mainly occurred within week 2 and 3 after radiotherapy start. Three other patients treated above Th8 reported no esophageal toxicity. There was a significant correlation between mean and maximum dose to the esophagus and reported toxicity. These results indicate that there is a high incidence of early esophageal toxicity, when irradiating vertebrae above Th8. A dose-effect relationship assessment was attempted, see Figure 1.

[figure not shown]

Figure 1 The risk of toxicity of the gastro-intestinal tract as a function of mean and maximum esophageal dose, as estimated using univariate logistic regression¹¹.

In most radiotherapy centers worldwide, simple radiotherapy techniques as one field or opposing fields are used to treat MSCC as this is the least resource craving techniques and treatment start is often the day as radiotherapy planning because of the urgent nature of MSCC. With these techniques sparing of the esophagus is not possible. Modern technology such as inversely modulated radiotherapy (IMRT) and volumetric arc therapy (VMAT) holds the potential for shaping the dose gradient smooth around the target and it is possible to prioritize avoidance of organs at risk. Furthermore, precise setup with Cone-Beam Computed Tomography (CBCT) enables the use of tighter safety margins for treatment.

Standard of care in our departments is VMAT and daily position verification with CBCT. Based on the dose response curves in Figure 1 we made VMAT dose plans that kept the maximum esophagus dose below 10 Gy when prescribing 30 Gy/10 fractions, see Figure 2.

[figure not shown]

Figure 2. Axial cut of a vertebra with VMAT dose color wash and delineation of esophagus. Red area represents high-dose area. Blue area represents low-dose area. A: standard dose plan. B: esophagus sparing plan. The arrow points at the esophagus.

Sparing of the esophagus can only be achieved by compromising dose to the vertebra and/or increasing the dose from angles that do not pass the esophagus thereby increasing dose to other organs, e.g. the lungs. In the present proposal we want to examine the clinical effect of this compromise.

Esophagus sparing radiotherapy prerequisites thorough delineation of the esophagus and can delay treatment start. If esophagus sparing radiotherapy is to become standard and disseminated, the process should be automated. Preferably, leaving only delineation of the target as a manual task. Automatization of the planning process will reduce waiting time for treatment and treatment time, both of which are important for these fragile patients.

1.3 Glucocorticoid-induced diabetes

High dose glucocorticoid is used in MSCC to decrease inflammation and edema in the affected vertebra and neural tissue. In our clinic, patients are started on high-dose glucocorticoids (150 mg Prednisolone daily) when MCSS is suspected. During radiotherapy the dose is reduced to 75 mg daily. A minimum 5 days of treatment are mandatory, even for patients treated with single fraction. High-dose glucocorticoid treatment may be discontinued after 5 days or after end of radiotherapy treatment, whichever comes first. Depending on symptoms and duration of prior glucocorticoid treatment some patients may benefit from a gradual decrease. ^{12,13}

It is well established that glucocorticoid treatment can induce new-onset hyperglycemia and even glucocorticoid-induced diabetes mellitus (GIDM) in patients without a history of diabetes mellitus (DM) ¹⁴. Hyperglycemia has been associated with complications such as longer hospital stays, delayed wound healing, increased infections and higher mortality rates. ¹⁴

As of now there are only two studies describing glucocorticoid-induced diabetes in patients receiving treatment for MSCC. ^{15,16} Schultz et al performed a prospective study including 131 patients receiving high-dose glucocorticoids for MSCC. The patients were monitored with 1-3 finger prick glucose measurements for 12 days after treatment start. 43% of the patients presented plasma glucose values diagnostic of diabetes and 12% were treated with insulin¹⁵. A HbA_{1c}-value <39 mmol/mol was associated with a negative predictive value of 96% for not developing diabetes needing treatment with insulin.¹⁵

While insulin-treated diabetes was mainly diagnosed in the first week after treatment start, the incidence of non-insulin treated diabetes was rising through-out the study period¹⁵. There are no data describing glucose levels beyond the study period of 12 days.

[figure not shown]

Figure 3 Time course of development of diabetes¹⁵

In patients that did not receive insulin, GIDM was left untreated.¹⁶ Out of 16 patients treated with insulin, 14 had blood glucose measurements >15 mmol/l before insulin treatment was initiated, the last two patients had insulin after blood glucose measurements >14.0 and 14.4 mmol/l.¹⁶ Development of insulin demanding diabetes was associated with reduced survival, suggesting either a metabolic effect of hyperglycemia on mortality or an underlying mechanism simultaneously promoting diabetes and mortality.¹⁶

The absence of international and national guidelines regarding treatment of glucocorticoid-induced hyperglycemia and diabetes in this patient cohort makes clinical treatment inhomogeneous as it mainly depends on the treating physician.

As an example, the local guidelines on management of glucocorticoid-induced hyperglycemia in the two centers participating in this study are different in their approach. The plasma-glucose threshold for considering treatment with insulin ranges from 11.1mmol/L-25 mmol/L in Herlev Hospital and Rigshospitalet respectively.^{12,17} Only one center uses a HbA_{1c}-value of <39 mmol/mol to identify patients that do not need glucose monitoring.¹² See Table 5 and 6 for guideline summary.

Patients with MSCC constitute a unique population making treatment of glucocorticoid-induced hyperglycemia especially challenging. The patients are fragile with a short life expectancy and often already heavily medicated in relation to their cancer diagnosis. It is desirable not to burden these

patients with unnecessary hospital contacts, blood sampling and medical treatment. As most patients will not live to experience any late diabetic complications, it is reasonable that focus should be on managing symptomatic hyperglycemia and preventing acute hyperglycemic complications. If the hyperglycemia is transient and asymptomatic, it would be preferable to spare the patient from supplementary burdensome glucose monitoring and insulin administration.

As of now there are no studies describing the spontaneous course of plasma-glucose levels in patients treated with high-dose glucocorticoids for MSCC during and after treatment completion.

Flash glucose measurement technology has been available on the Danish market for approximately 5 years.¹⁸ The FreeStyle Libre system uses a factory calibrated sensor placed on the upper arm. The sensor provides glucose measurements every 15 minutes, these can be read by swiping the sensor with a reading device or a smartphone with a preinstalled app. Retrospective glucose data analysis can then be generated using the system software¹⁹. Because the sensor is factory calibrated, it can be worn for 14 days with no required intervention e.g. finger prick glucose measurements.

A blinded Flash sensor is available for professional use (FreeStyle Libre Pro™; Abbott Diabetes Care, Witney, UK).²⁰

In this this study we wish to address two issues regarding glucocorticoid-induced diabetes.

Firstly, the dose and duration of glucocorticoid-treatment has been reduced significantly since 2014 where the study by Schultz et al was performed. The use of HbA1c < 39 mmol/mol as a cut-off to identify the patients at low risk of developing insulin demanding diabetes needs to be validated in this new setting.

Secondly, we wish to characterize the spontaneous course of plasma-glucose during and after high-dose glucocorticoid treatment using Flash patients with MSCC with no prior history of diabetes.

2 ESO-SPARE

We propose a phase III trial – ESO-SPARE, with randomization to esophagus sparing radiotherapy or standard of care radiotherapy for patients treated for MSCC in the thoracic and cervical spine. The primary aim of ESO-SPARE is to examine if advanced radiotherapy planning and delivery of radiotherapy with sparing of the esophagus can decrease patient reported esophageal toxicity.

Concurrently we want to conduct a observational study of glucocorticoid diabetes in patients with metastatic spinal cord compression (the GLUC-DIAB study). In this study we wish to characterize the spontaneous course of blood-glucose level during and after high-dose glucocorticoid treatment and validate the HbA_{1c} cut-off used in the clinic to identify patients in low risk of developing glucocorticoid-induced insulin-dependent DM.

We have the following research questions:

- Can esophagus sparing radiotherapy significantly decrease patient reported esophageal toxicity in patients with metastatic spinal cord compression without compromising their ambulatory function?
- Will esophagus sparing radiotherapy increase other toxicities compared to standard radiotherapy?
- What is the spontaneous course of blood-glucose level during and after high-dose glucocorticoid treatment for patients with MSCC?
- What is the incidence of glucocorticoid-induced diabetes in patients with MSCC?
- How many of the patients that develop glucocorticoid-induced diabetes, have normalized their plasma-glucose values on day 28 after start of glucocorticoid treatment?
- Can HbA1c be used as a negative predictive value for not developing insulin demanding diabetes?
- What is the incidence of hospital admissions due to new-onset diabetes?

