2.6 HbA_{1c} validation

Baseline HbA_{1c} is measured for all patients starting high glucocorticoid treatment for MSCC. Baseline values above 48 mol/mol are considered diagnostic for DM. For all other patients, diabetes developed during glucocorticoid treatment will be defined as two random plasma glucose measurements ≥ 11 mmol/L. Based on baseline HbA_{1c} results and subsequent glucose measurements from the patients included in ESO-SPARE we will validate if the current HbA_{1c} cut off value (39 mmol/mol) can identify patients in low risk of developing glucocorticoid-induced insulin-dependent DM.

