9.1 Ethical considerations

The focus of this study is palliation with reduction of side effects from necessary radiation therapy for MSCC. The study participants are fragile with low life expectancy.^{2,5} In order to minimize the time, spend in hospital, we designed the study with electronical/telephone follow-up only.

All toxicology data will be collected as patient reported outcomes (PRO). All though we will not act directly the collected PRO, the patients will be encouraged to contact the department with any problems there might occur.

In order to compute a radiation plan with sparing of the esophagus for patients in the experimental arm, it might be necessary to compromise the dose delivered to the anterior part of the vertebra close to the esophagus. While we do not expect the treatment in the experimental arm to be less effective, it is one of the objectives of this study to examine this. Reirradiation rates in the two arms will be assessed continuously. The TMC can recommend cessation of the study or dose adjustments if the reirradiation rate in the experimental arm is to excessive.

There will be no extra radiation from extra scans in this study.

In order to determine the natural course of plasma-glucose during and after high-dose glucocorticoid treatment, we wish to perform a real-life study with as little intervention as possible. Therefore, we intend to use blinded glucose measurements only. For study participants 1-2 fewer glucose measurements pr. week compared to current standard is expected. Patients participating in

the study by Schultz et al received 300 mg Prednisolone daily for 10 days, which was local standard at the time.¹⁵ The guidelines have since been modified and currently recommended Prednisolone doses as well as duration of treatment is significantly lower.¹³ Because of this, we expect the incidence of glucocorticoid induced hyperglycemia and diabetes to be lower in our study population.

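### The HbA1c cut-off to be validated is written both as below 39 and as 39 or below, and the only accuracy measure named, negative predictive value, cannot by itself show that the cut-off separates risk

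*Protocol*

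**What the plan says.** The research questions in Protocol Section 2 ask "Can HbA1c be used as a negative predictive value for not developing insulin demanding diabetes". Section 1.3 gives the precedent: in a prospective cohort of 131 patients, a value below 39 mmol/mol "was associated with a negative predictive value of 96% for not developing diabetes needing treatment with insulin", and "12% were treated with insulin". It then explains why revalidation is needed, namely that steroid dose and duration have since been reduced.

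The cut-off appears in three forms.

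- Section 1.3 has it strictly below 39: "The use of HbA1c < 39 mmol/mol as a cut-off to identify the patients at low risk". On current practice, the same section says "Only one center uses a HbA_{1c}-value of <39 mmol/mol to identify patients that do not need glucose monitoring" and points to Tables 5 and 6.
- Section 2.6 gives no sign: "we will validate if the current HbA_{1c} cut off value (39 mmol/mol) can identify patients in low risk".
- Section 7, Table 5 (Herlev Hospital) assigns no glucose measurements to patients at 39 or below. Its next band is 40–47.

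Section 2.6 names no accuracy measure, interval or comparison. Sensitivity and specificity are not mentioned in either document, and the SAP does not cover the HbA1c validation. Section 2.3 does list the incidence of insulin-treated glucocorticoid-induced diabetes as a secondary endpoint. On expected event rates, Section 9.1 says "we expect the incidence of glucocorticoid induced hyperglycemia and diabetes to be lower in our study population" and gives no figure. Section 3.2 sets the sub-study at 150 patients without a calculation.

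**The concern.** There are two separate problems.

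The first is the definition. A validation should test the rule that is in use. If the analysis takes below 39 from Section 1.3 while the centre applies 39 or below from Table 5, patients at exactly 39 count as higher risk in the validation but as low risk in the practice being validated.

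The second is the measure. NPV depends on how common the outcome is. A marker that carries no information still has an NPV of 1 − incidence, because the patients below its cut-off have the same risk as everyone else. The reduction in steroid exposure that prompts the revalidation is also the reason the protocol gives for expecting less hyperglycaemia and diabetes. If insulin-treated cases fall as well, NPV rises whether or not HbA1c discriminates. The study could then report a reassuring NPV, and the cut-off could be taken as confirmed, without evidence that risk differs on its two sides. What is at stake is a conclusion about which patients can go without glucose monitoring.

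**Working it through.** **The protocol's own figure.** Section 1.3 reports 131 patients and 16 treated with insulin (the 16 comes from the companion report, assumed to be the same cohort). 16/131 = 12.2%, which agrees with the stated 12%. The earlier NPV of 96% cannot be reproduced, because the documents give no two-by-two counts.

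**NPV of an uninformative marker.** Formula: NPV = 1 − incidence. Only the 12% comes from the documents; the lower incidences are assumptions. The last column is the binomial probability of at most 3 events in 75 patients (72/75 = 96%), that is, the chance that a useless marker shows an NPV of at least 96%. It assumes that half of the 150 fall below the cut-off.

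| Incidence of insulin treatment | Uninformative NPV | Expected cases in 150 | Chance of observed NPV ≥ 96% in 75 |
|---|---|---|---|
| 12% (earlier cohort) | 88% | 18 | 0.02 |
| 10% (assumed) | 90% | 15 | 0.05 |
| 8% (assumed) | 92% | 12 | 0.14 |
| 6% (assumed) | 94% | 9 | 0.33 |
| 4% (assumed) | 96% | 6 | 0.65 |

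In the earlier cohort the uninformative level was 1 − 0.122 = 87.8%, so 96% stood about 8 points above it. Suppose HbA1c keeps the accuracy implied by those figures. The odds of insulin treatment below the cut-off were 0.04/0.96 = 0.0417 and overall 0.122/0.878 = 0.1390, a ratio of 0.300.

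- At 6% incidence the odds below the cut-off become 0.300 × 0.06/0.94 = 0.0191, so NPV = 1/1.0191 = 98.1%, against 94% for a useless marker.
- At 4% they become 0.300 × 0.04/0.96 = 0.0125, so NPV = 1/1.0125 = 98.8%, against 96%.

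The gap to be detected shrinks from about 8 points to about 3–4.

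**Precision.** An observed 72/75 = 96% has an exact 95% interval of 88.8–99.2%. With 90 of 150 below the cut-off (assumed) and 4 events, 86/90 = 95.6% has an interval of 89.0–98.8%. At 4–6% incidence, each interval contains both the uninformative and the informative value.

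**Patients at exactly 39.** HbA1c is assumed normal and rounded to whole units, with entry restricted to values below 48. The share at 39 is P(38.5 < X < 39.5)/P(X < 47.5).

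- Mean 36, SD 5: 6.7%, or 10 of 150.
- Mean 38, SD 4: 9.7%, or 15 of 150.
- Mean 40, SD 4: 9.9%, or 15 of 150.

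Over means of 36–40 and SDs of 4–5 the range is about 7–10%, or 10–15 patients.

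**The case against.** The strongest defence is that NPV suits the purpose. The question is one of rule-out, and the absolute risk below the cut-off answers it directly. The comparator is also already planned, since the incidence of insulin-treated diabetes is a secondary endpoint and anyone can subtract it from 1. Both points stand: choosing NPV is not an error. What is missing is any instruction to read it against that incidence.

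Three stronger readings are tempting, and the documents do not support them.

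- A reader might infer that the incidence the protocol expects would by itself give an uninformative marker an NPV of 94–96%. That needs 4–6%, a fall of one half to two thirds from 12%. Section 9.1 gives no figure and speaks of hyperglycaemia and diabetes; the earlier diabetes figure is 43%, and the 12% is insulin treatment. A fall in insulin-treated cases is a reasonable inference, but only that. A modest fall to 8–10% gives 90–92%, visibly below the earlier 96%.
- A reader might infer that validation will rest on NPV alone. Section 2.6 names no measure, so this is an inference from silence.
- A reader might take 96% as the pass mark. It is reported only as an earlier result.

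A further fair objection is that adding sensitivity will not rescue a small number of events. With 6–9 cases, a sensitivity of 5/6 has an exact 95% interval of 36–99.6%, and 7/9 has 40–97%. That also stands, and the report should say so.

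The conflict over the sign has no good answer: Section 1.3 and Table 5 both describe clinic practice and disagree for a patient at exactly 39.

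**Conclusion.** The point holds in a limited form. The inconsistency in the cut-off is on the page and could move about 10–15 of 150 patients between groups; that number depends wholly on the assumed HbA1c distribution, and its effect on NPV cannot be calculated from the documents. No plan for measuring performance is given beyond the mention of NPV. Without a comparison with 1 − incidence, a high NPV would not show that the cut-off separates risk. How misleading it could be depends on an incidence the protocol does not state: little at 12%, where a useless marker would seldom reach 96%, and considerably at an assumed 4–6%. Severity is minor. This is a secondary question in the observational sub-study, and the randomised comparison is unaffected.

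**What to change.** - Reconcile Section 1.3, Section 2.6 and Table 5 on the sign of the cut-off, and state the agreed form once. Run the validation at both below 39 and 39 or below, and report both.
- Report NPV with an exact 95% interval beside 1 − incidence, taking the incidence from the existing secondary endpoint.
- Add sensitivity, and the difference in incidence of insulin-treated diabetes between patients below and above the cut-off, each with an exact 95% interval. Base the conclusion on this comparison rather than on the level of NPV.
- State in advance that few events are likely (6–9 of 150 at an assumed 4–6%), that the estimates will be imprecise, and that the result may be inconclusive.

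The cost is a few lines of analysis text, in the protocol or in a short analysis plan for the sub-study. No new data are needed. The change guards against over-reading the result; it does not add power.
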